- g. Did the suction tube remain in place in the uterus until removal (Yes/No/Unknown)
- h. Did the suction tube establish a good seal (no loss of suction) (Yes/No/Unknown)
- Did the suction tube interfere with or facilitate examination for and management of lower genital tract bleeding after vaginal birth (Facilitated/Interfered/Neither/not applicable/Unknown)
- j. Did the suction tube interfere with or facilitate surgical exposure during caesarean birth (Facilitated/Interfered/Neither/Unknown)
- k. Was there any blockage of the suction tube (Yes/No/Unknown)

Recruitment and consent

We plan to approach women at increased risk of PPH awaiting caesarean or induction of labour, pre-labour or in early labour and provide written and/or video information to them. They will be given time to discuss participation with friends and family and then invited to provide signed consent. Consent will be confirmed verbally immediately after birth, prior to device insertion.

Sample size

We aim to use the U-STAT in 40 participants, with a minimum of 25% being vaginal births and 25% caesarean section. 35 participants will provide 90% confidence that the true rate of adverse device effects and device deficiencies is under 10% (+/-10%). The sample is increased to 40 to account for any unexpected procedural difficulties in the first 5 recruits.

Procedures

Participating sites will be supplied with a 'PPH emergency trolley' containing all the supplies needed for STUT and emergency treatment of PPH, as well as forms for screening, enrolment, randomization and data collection. After vaginal birth, the suction tube will be inserted under sterile conditions transvaginally into the uterine cavity. Suction will be applied either with the manual suction device or with a surgical suction unit, set at 100mmHg suction pressure. If there is excessive bleeding which is not controlled by the STUT, the suction tube will be removed and management continued according to local protocols. If effective, the STUT suction will be interrupted every 30 minutes, and removed as soon as bleeding is controlled without suction. All other care will follow local practice. Blood loss will be measured from enrolment until bleeding is controlled (minimum 30 minutes), using a blood collection drape or Maternawell tray, plus blood collected in the UVT suction bottle, surgical suction and swabs.

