19. Tamponade device inserted? 2=Other tube*; 3=Ellavi; 4 = Other	· ·				
20. Time device inserted:		:			

21. Ease of insertion? 1=easy, 2=mod.diff, 3=difficult		
22. Device stable in uterus? 0=No; 1=Yes		
23. Tube air leak? 0=No; 1=Yes; 3=No tube		
25. Effect of device on exam/mx? 1. Facilitated, 2. Interfered, 3.Neither		
26. Exam obscured by blood from ut: 0=No; 1=Yes		
27. Time bleeding stopped.	:	
28. Time vital signs check (+ 15min)	:	
29. Syst BP mmHg		
30. Diast BP mmHg		
31. Pulse /m		
32. Additional oxytocin 0 = No 1= Yes		
33. Additional erg-/syntomentrine 0 = No 1= Yes		
34. Additional misoprostol 0 = No 1= Yes		
35. Additional tranexamic acid 0 = No 1= Yes		
36. Time blood collection measured (>30 min)	:	
37. Blood volume excluding suction jar (ml)		
38. Blood volume in suction jar (ml)		
39. Blood expelled ex ut. after removal of device or after 30 min in control group (ml)		
40. If bleeding persists, measured blood loss post 30min		
41. Laparotomy 0 = No 1= Yes		
42. Compression sutures 0 = No 1= Yes		
43. Uterine devascularization 0 = No 1= Yes		
44. Hysterectomy 0 = No 1= Yes		
45. Other procedure 0 = No 1= Yes*		
46.ICU admission 0 = No 1= Yes		
47. Organ failure 0 = No 1= Yes*		

48. Death 0 = No 1= Yes		
49. Blood transfusion (number of units RBCs)		
50. First Haemoglobin after bleeding controlled (g/dL)		
51. Highest temperature (deg C)		
52. Endometritis 0 = No 1= Yes 9=Unknown		
53. Other complications 0 = No 1= Yes* 9=Unknown		
53. Date of Discharge (DD/MMM/YY)	/ /	

Completed by (initials) :	Date completed	(dd/mmm/yy)
Completed by (initials) .	Date completed	(dd/IIIIIII/yy

Vaginal birth Clinical checklist (remains in hospital records)

Equity for Suction Tamponade Access to treat postpartum haemorrhage: The ESTA project

	1.	○ Consent signed
	2.	Confirm with Mother that still happy with consent
	3.	Ostudy trolley is available with register, U-STAT suction tubes, working suction
	4.	Clean drape or Maternawell tray available
	5.	\bigcirc Manual suction device ready with vacuum pumped or suction machine pressure set to 100mmHg – block tubing to check
	6.	After baby born position drape/Maternawell tray below the buttocks
Aft	er p	lacenta delivered completely:
	7.	Examine vaginally to exclude major lower genital tract trauma
	8.	O Note the time, 24 hr: H H : M M
	9.	○ Open next numbered envelope and note allocation: ○ STUT* ○ Control
	10.	*Insert U-STAT tube to fundus of uterus and start suction

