	11.	\bigcirc *Insertion of tube; \bigcirc easy, \bigcirc moderately difficult, \bigcirc difficult, \bigcirc Failed, \bigcirc not done
	12.	Alternative Management
	13.	*Time tube insertion procedure completed 24 hr: H H : M M
	14.	*Check tube/balloon stable in uterus Yes / No / Onot used
	15.	Ocontinue routine care including repair of bleeding tears
	16.	*Effect of device on exam/mx of lower genital tract bleeding? Facilitated; Interfered; Neither; Unknown
	17.	○ Note the time per vaginal bleeding stopped. 24 hr: H H : M M
	18.	○ 15 minutes after insertion (10 above) note time 24 hr: H H : M M
		Systolic BP Diastolic Pulse
	19.	○ 30 minutes after insertion, note time. 24 hr: H H : M M
	20.	
		ml ml
	21.	Replace empty tray, expel blood from the uterus by fundal massage (into tray)
	22.	○ Measure blood loss in tray = RESIDUAL
		ml ml
	23.	*disconnect suction. If no bleeding in 10 minutes, remove U=STAT tube
	2/	*If bleeding continues replace empty tray continue suction plus other measure

25. When bleeding stopped, measure blood loss in tray = Secondary blood loss
ml ml
26. *Measure blood loss in suction bottle
ml ml
27.
○ None
The participants will be followed till discharge and the outcome data, as well as any complications, recorded.

Caesarean birth Clinical checklist (remains in hospital records)

Equity for Suction Tamponade Access to treat postpartum haemorrhage: The ESTA project

	1.	○ Consent signed
	2.	Oconfirm with Mother that still happy with consent
	3.	OStudy trolley is available with register, U-STAT suction tubes, working suction
	4.	Clean drape or Maternawell tray available for post-op use
	5.	○ Manual suction device ready with vacuum pumped or suction machine pressure set to 100mmHg – block tubing to check
	6.	\bigcirc After birth of baby, open next numbered envelope and note allocation: \bigcirc STUT* \bigcirc Control
Aft	er p	placenta delivered completely:
	7.	○ Note the time, 24 hr: H H : M M
	8.	\bigcirc *Insert U-STAT tube to fundus of uterus and lower end through cervix and vagina, ask assistant to connect and start suction
	9.	\bigcirc *Insertion of tube; \bigcirc easy, \bigcirc moderately difficult, \bigcirc difficult, \bigcirc Failed, \bigcirc not done
	10.	. Alternative Management
	11.	. *Time tube insertion procedure completed 24 hr: H H : M M
	12.	. Continue uterine closure
	13.	*Effect of device on visualisation for uterine closure? \(\text{Facilitated}; \text{Interfered}; \) Neither; \(\text{Unknown}\)

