	14.	. Time uterus closed 24 hr: H H : M M
	15.	. Measure blood volume in suction bottle = pre-suction volume:
		ml ml
	16.	*Note the time bleeding through suction tube stopped. 24 hr: H H : M M
	17.	. O 15 minutes after placental delivery (7 above) note time 24 hr: H H : M M
		Systolic BP Diastolic Pulse
	18.	. After skin closure, estimate surgical blood loss (excluding U=STAT tube drainage)
		ml ml
	19.	. O In recovery room: Place drape or Maternawell tray under participant's buttocks
	20.	
	21.	. O 30 minutes after placental delivery (7 above), note time. 24 hr: H H : M M
	22.	. Swab vagina and measure blood loss in drape/tray = postop blood blood

23. O Place new tray or drape under participant and express blood from uterus -
Measure blood loss in drape/tray = RESIDUAL blood
ml ml
24. *Disconnect suction, if no bleeding after 10 minutes, remove U-STAT tube. If
bleeding resumes, reconnect suction and manage as per hospital protocol
25. *Measure blood loss in suction bottle
ml ml
26. *Suction tube problems: Fell out; blocked; leaking; Poor suction
○ None

ml

The participants will be followed till discharge and the outcome data, as well as any complications, recorded.

Participant questionnaire (Vaginal birth Intervention group only)

Protocol Title: Equity for Suction Tamponade Access to treat postpartum haemorrhage: The ESTA project			
Site Number:	Subject ID:	Date:(dd/mmm/yy)	
Dear Participant, thank you for assisting us with the ESTA project. Pease would you answer the following questions. There are no right or wrong answers. Please just give us your personal opinions. Please feel free not to answer if you prefer not to.			
Questionnaire		Comment/Notes	
*After the hirth of your ba	by a tubo was	T	
*After the birth of your baby, a tube was inserted to your uterus to help reduce bleeding Please could you describe the pain you experienced? 0=No pain; 1 = Mild pain; 2 = Severe pain; 3 = Unbearable pain; 4 = unsure; 9 = no data			
*Please could you describe when the tube was removed = Mild pain; 2 = Severe pain Unbearable pain; 4 = unsure	d? 0=No pain; 1 u; 3 =		
*Please could you describe overall about the suction tub 0= fine; 1 = uncomfortable b = Unacceptable; 3 = Unbear unsure; 9 = no data	pe procedure? out acceptable; 2		
Thank you for assisting with this questionnaire			

Date completed

(dd/mmm/yy)

Completed by (initials):

Participant questionnaire (Caesarean birth Intervention group only)

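### At caesarean no vessel is specified under the participant until recovery, so vaginal loss in theatre is largely captured through the tube in the device arm but has no stated collector in controls

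*Protocol*

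**What the plan says.** The Procedures section gives a general rule: "Blood loss will be measured from enrolment until bleeding is controlled (minimum 30 minutes), using a blood collection drape or Maternawell tray", supplemented by the suction bottle, surgical suction and swabs. Under Quality assurance (During recruitment), enrolment is immediately after the baby is born.

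The Caesarean birth Clinical checklist handles the vessel differently:

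- Item 4 (both arms): "Clean drape or Maternawell tray available for post-op use".
- Item 8 (device arm): the tube is placed at the fundus with its lower end through cervix and vagina, and the operator is to "ask assistant to connect and start suction". This comes before uterine closure.
- Item 18 (both arms): "After skin closure, estimate surgical blood loss (excluding U=STAT tube drainage").
- Item 19 (both arms): "In recovery room: Place drape or Maternawell tray under participant's buttocks".
- Item 21: the 30-minute reading is timed from placental delivery.
- Items 22 and 23 (both arms): the vagina is swabbed, the tray is read, and blood is then expressed from the uterus and measured.
- Item 25 (starred, so device arm only): "Measure blood loss in suction bottle".

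The Vaginal birth Clinical checklist puts the vessel in place before allocation: "After baby born position drape/Maternawell tray below the buttocks" (item 6).

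The outcomes affected are secondary outcomes 1–3: loss within 30 minutes, loss above 500 ml and loss above 1000 ml. They are to be compared as mean differences or risk ratios with 95% confidence intervals and no p values.

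**The concern.** Once the uterus is closed, blood from the cavity leaves through the cervix and vagina in both arms. In the device arm a suction tube lies in that route and empties into a measured bottle. In controls the same blood can run out in theatre with nothing specified to catch it. Theatre time lies inside the 30-minute window, so the same physiological loss may be counted in one arm and partly uncounted in the other.

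The study is meant to indicate effectiveness and suitability for a larger randomised trial. A systematic measurement difference between arms is not reduced by a larger sample, and it would carry forward if the same checklist were reused. Blood that was not collected cannot be restored at analysis.

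**Working it through.** The protocol states no figure for this point, so there is none to reproduce. The check has two parts.

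**1. Where each component of loss is recorded at caesarean**

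| Blood | Device arm | Control arm |
|---|---|---|
| Drained through the tube from item 8 | Bottle, item 25 | Not applicable |
| In the suction bottle at uterine closure | Item 15 | Item 15 |
| Surgical loss in theatre | Estimate, item 18 | Estimate, item 18 |
| Out of the vagina in theatre, not through a tube | No stated collector | No stated collector |
| Still in the vagina at 30 minutes | Item 22 | Item 22 |
| Still in the uterus at 30 minutes | Item 23 | Item 23 |

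The fourth row is empty in both arms, but it does not hold the same blood. In the device arm it holds what passes around the tube, or escapes when the tube leaks, blocks or falls out. In controls it holds all vaginal loss in theatre. Item 15 is read at uterine closure, before the gap opens. Item 20 is not legible in the text, but it follows tray placement and so cannot supply earlier collection. The case record form (items 37–40) has no separate line for vaginal loss in theatre.

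**2. Scale, under stated assumptions**

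Inputs from the protocol:
- caesarean loss of mean 558 ml, SD 496 ml (Background);
- at least 25% vaginal and 25% caesarean births (Sample size), so caesareans are 25–75%, or 10–30 of 40 per arm.

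Assumptions: no true device effect, and a net volume v missed per control caesarean beyond what is missed with the device. The protocol does not give v. I use 50–150 ml for illustration; it could be near zero.

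*Mean difference.* The caesarean shift equals v, so 50–150 ml. The overall shift is v × caesarean share: 50 × 0.25 = 12.5 ml up to 150 × 0.75 = 112.5 ml.

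*Random error.* The 95% half-width for the caesarean mean difference is 1.96 × 496 × √(2/n): 435 ml at n = 10 per arm, 307 ml at n = 20 and 251 ml at n = 30. The shift is smaller than each of these.

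*Risk ratios, caesareans only.* With a log-normal matched to 558/496, the null risk ratio for threshold c is P(X > c) / P(X > c + v).

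| v (ml) | >500 ml | >1000 ml |
|---|---|---|
| 0 | 1.00 | 1.00 |
| 50 | 0.406/0.358 = 1.13 | 0.126/0.113 = 1.11 |
| 100 | 0.406/0.317 = 1.28 | 0.126/0.102 = 1.24 |
| 150 | 0.406/0.280 = 1.45 | 0.126/0.092 = 1.37 |

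The ratios use unrounded probabilities. The fitted curve puts 6.8% above 1300 ml where the protocol reports 5%, so it is approximate. These ratios would be diluted in the whole trial. By how much cannot be computed, because the protocol gives no distribution of loss after vaginal birth.

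*Time without a vessel.* The protocol gives no operating times. If the uterus were closed 8–15 minutes after placental delivery and recovery reached at 25–40 minutes, the uncollected time is min(recovery, 30) − closure. That runs from 25 − 15 = 10 to 30 − 8 = 22 minutes, or 33–73% of the window. Recovery later than 30 minutes would also break the checklist order, since item 19 precedes item 21. Minutes without a vessel do not convert into millilitres.

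**The case against.** The strongest replies are these.

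- **The tray is absent in theatre in both arms.** This stands. A reader might infer that only controls are under-measured; the checklist does not support that, because blood bypassing the tube is equally uncollected. What remains is a difference in how much is missed.
- **Item 18 may already cover it.** Its only stated exclusion is tube drainage, so for a control nothing is formally excluded and visible vaginal loss might be added. This stands in part. The item is worded as surgical loss and does not mention the vaginal route, so staff could reasonably do either. It is also an unblinded estimate, which could err in either direction.
- **The conflict with Procedures is soft.** The from-enrolment sentence sits in a paragraph that opens with vaginal birth, and caesarean placement is described afterwards. However, the sentence lists surgical suction and swabs, which suggests that it covers caesarean too. The differential gap does not depend on this sentence, because it follows from the checklist alone.
- **These are secondary outcomes in a small pilot without p values.** This stands. The primary outcome is device effects and deficiencies, and the main efficacy outcome is active bleeding beyond 10 minutes. Haemoglobin change and transfusion do not depend on the tray either.

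**Conclusion.** The point holds as a differential measurement gap in secondary outcomes 1–3 among caesarean births. Followed as written, the checklist captures most theatre vaginal loss in the device arm and names no collector for it in controls. This component tends to make the device look worse.

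Two stronger readings are tempting but not supported. One is that the blood-loss comparison as a whole is biased against the device: bypass around the tube and the unblinded estimate at item 18 leave the net direction uncertain. The other is that the gap would mislead the decision on a larger trial: the missed volume is undocumented, and the outcomes that lead the assessment are not volumes.

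If 50–150 ml were missed per control caesarean, the shift would be that amount in caesareans and about 13–113 ml overall at 25–75% caesareans. It would usually sit within random error, but the confidence interval would not show it. All these sizes rest on the assumed volume, and the risk ratios also on the log-normal shape. The gap is worth closing before recruitment because it cannot be repaired afterwards.

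**What to change.** Reconcile caesarean checklist items 4, 18 and 19 with the rule that loss is measured from enrolment:

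1. In both arms, collect vaginal loss in theatre from placental delivery until the recovery tray is placed, using the same drape or pad under the buttocks, read or weighed before transfer.
2. Record it on its own line in the checklist and case record form, and add it to total loss in both arms.
3. State in item 18 that the surgical estimate excludes this volume, so that it is not counted twice.
4. Keep the recovery tray as now.

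The cost is a checklist and form edit plus one extra reading per caesarean. If pads are weighed, this adds a step that the protocol does not currently describe. A drape or pad already in place before birth will also collect some amniotic fluid. That contamination should be balanced between arms, because allocation follows birth, but it should be noted, or avoided by placing or changing the pad after birth where feasible. The change concerns measurement only.

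### The caesarean checklist prompts no tray or drape reading after about 30 minutes, at odds with Procedures, CRF item 40 and the vaginal checklist, so late blood loss may be missed

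*Protocol*

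**What the plan says.** **Protocol, Procedures.** "Blood loss will be measured from enrolment until bleeding is controlled (minimum 30 minutes), using a blood collection drape or Maternawell tray", together with the suction bottle, surgical suction and swabs. No distinction is made by arm or mode of birth.

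**Protocol, Clinical Record Form.** Item 36 reads "36. Time blood collection measured (>30 min". Item 39 reads "39. Blood expelled ex ut. after removal of device or after 30 min in control group (ml". Item 40 reads "If bleeding persists, measured blood loss post 30min". None of these is limited to one mode of birth, and items 36 and 40 are not limited to one arm.

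**Protocol, Vaginal birth Clinical checklist.** After the residual reading (item 22), item 25 is unstarred: "When bleeding stopped, measure blood loss in tray = Secondary blood loss". The instruction to put an empty tray in place beforehand sits in item 24, which is starred.

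**Protocol, Caesarean birth Clinical checklist.** The drape or tray is read 30 minutes after placental delivery (items 21-22), and expressed blood is then read as the residual (item 23). Item 24, starred, says that if "bleeding resumes, reconnect suction and manage as per hospital protocol". Item 25, also starred, records the suction bottle. No tray or drape reading follows.

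In both checklists the star is attached to the STUT allocation where the envelope is opened, so starred items belong to the device arm.

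**Protocol, Outcomes.** Secondary outcome 1 covers 30 minutes from insertion. Outcomes 2 and 3 (>500 ml and >1000 ml) state no window.

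**The concern.** The rule in Procedures and the bedside form do not match for caesarean births. The attending clinician completes the checklist at the time of care, and it becomes part of the patient's record. Research staff fill in the CRF and check it against patient records (Protocol, During recruitment). If the checklist does not prompt for a fresh tray and a later reading, CRF item 40 may be left blank or filled by estimate.

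The women affected are those still bleeding after 30 minutes, whose total loss is most incomplete if measurement ends there. The gap also differs between arms. The device arm has a bottle volume that may include part of the late loss; controls have no later volume at all. And it differs between modes of birth, since the vaginal form does prompt for late loss. Totals pooled over mode could then cover different periods.

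**Working it through.** No published figure needs reproducing, and no formula applies; the check is a comparison of the forms.

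| Step | Vaginal checklist | Caesarean checklist |
|---|---|---|
| Reading at 30 minutes | Time at item 19, then reading | Items 21-22, both arms |
| Residual blood | Items 21-22, both arms | Item 23, both arms |
| Time bleeding stopped | Item 17, both arms | Item 16, starred and tied to flow through the tube |
| Empty tray if bleeding continues | Item 24, starred | None |
| Tray reading when bleeding has stopped | Item 25, both arms | None |
| Suction bottle | Item 26, starred | Item 25, starred |

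1. **Caesarean, control arm.** After item 23 every volume item is starred. The checklist therefore gives a control neither a time at which bleeding stopped nor a volume after the residual reading. Both are needed to meet the Procedures rule.

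2. **Caesarean, device arm.** The bottle at item 25 is listed after the step at which suction may be reconnected, so it may include late loss through the tube. Loss around the tube or after its removal has no line. The device arm's late loss is therefore captured in part at best.

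3. **CRF item 40.** It asks for loss after 30 minutes whatever the mode of birth. At vaginal birth, checklist item 25 supplies it. The caesarean checklist has no matching line.

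4. **Vaginal, control arm.** Item 22 reads the residual blood in the tray. The replacement of that tray is in starred item 24, so as written it is not an instruction for controls. Item 25 then reads the tray in controls with the residual blood still in it. If items 22 and 25 are both added into a total, the residual blood is counted twice. This would raise recorded loss in vaginal controls, whereas the caesarean gap would lower it in caesarean controls.

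5. **Outcomes exposed.** Outcome 1 ends at 30 minutes by definition and is untouched by missing later loss. Total loss to control of bleeding is exposed. Outcomes 2 and 3 are exposed only if their window runs past 30 minutes, which the protocol does not say.

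6. **Number exposed.** Sample size sets a minimum of 25% for each mode among 40 device participants: 0.25 × 40 = 10 caesareans at least, and 40 − 10 = 30 at most. A similar number of controls is assumed, because allocation is in balanced blocks stratified by mode of birth. Only those still bleeding after about 30 minutes are affected. The protocol gives no rate for this, so the calculation stops here.

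**The case against.** The strongest reply is that the governing text already covers late loss. Procedures requires measurement until control in everyone, CRF item 40 applies to everyone, and the CRF, not the checklist, holds the outcome data. The checklist is only one part of the patient record, and caesarean item 23 puts a new tray or drape under women in both arms without saying that measurement then ends. This stands to the extent that the checklist sets no rule to stop measuring. It does not remove the mismatch: the vaginal form carries a prompt for the same requirement and the caesarean form does not.

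A reader might infer that late loss at caesarean is captured only through the device bottle, and that the >500 ml and >1000 ml outcomes are therefore cut short in controls. The documents do not support that. Procedures and CRF item 40 still call for late loss in both arms, the device arm also lacks a line for part of its loss, the bottle item gives no reading time, and outcomes 2 and 3 have no stated window. If that window is 30 minutes, late loss does not enter them.

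Nor does the caesarean mean of 558 ml (± 496 ml) cited in Background show that many women cross 500 ml after 30 minutes. With that mean, passing 500 ml is likely to be common without persistent bleeding.

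Some form content is missing from the copy read here. Caesarean item 20 has no text, but it precedes the 30-minute step. A stray volume box after item 26 probably belongs to item 22. Neither changes the reading.

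**Conclusion.** The inconsistency is established: the caesarean checklist does not carry the late measurement that Procedures, CRF item 40 and the vaginal checklist provide for. The consequence is a risk of incomplete capture, wholly in controls and partly in the device arm, among caesarean women still bleeding after 30 minutes. A net bias between arms is possible but not shown, and neither its size nor its direction can be calculated from the protocol.

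This rests on reading the star as marking the device arm and on staff following the checklist as written. It is a minor correction. The outcomes are secondary, the study is exploratory and reports no p values, and the primary outcome (device effects and deficiencies) is not affected. It is still worth making before recruitment, because analysis cannot restore a volume that was never measured.

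**What to change.** These changes concern measurement only; they alter no clinical step.

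1. **Caesarean checklist, after item 24.** Add an unstarred line for both arms: if bleeding continues or resumes, place an empty tray or drape; once it has stopped, note the time and record the volume as secondary blood loss. Direct this to CRF item 40.
2. **Vaginal checklist, item 24.** Separate the tray replacement from the suction instruction and remove its star, so that item 25 in controls starts from an empty tray and does not count the residual blood again.
3. **Outcomes 2 and 3.** State one window that applies to both arms and both modes of birth, and list the volume items that make up the total.

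The cost is one added line, one asterisk and one sentence of definition, plus a few minutes of measurement in the women still bleeding after 30 minutes.
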